10.5 Safety Assessments

Professors [name] and [name], together with [name] and designated study personnel will monitor each participant for adverse events during the study. All adverse events reported between consent and final follow-up will be recorded in the Case Report Form (CRF). Members of the project team will ask the participant non-leading questions in an effort to detect adverse events. Examples of this are:

"How are you feeling?"

Or

"Since you were last asked, have you felt unwell or different from usual?"

In addition, participants should be encouraged to spontaneously report any medical illness, or new symptoms.

10.6 Biomarker Studies

All participants will be asked to donate blood at each follow-up. The blood samples will be principally used for assay of measures of the function of blood immune cells, as well as markers in serum such as 25(OH)D. Gene expression patterns in the blood cells will also be studied. The kinetics of changes in any of these biomarkers due to phototherapy will be analysed. In the healthy controls, gene expression patterns (transcriptome analyses of cells in whole blood) and vitamin D levels in serum will be measured.

Permission will be sought from the patients diagnosed with CIS to use samples of blood to create a serum, whole blood, DNA, and RNA bank for subsequent scientific studies related to MS progression.

11. Advertising

There will be no advertisements for participants of this study, except for the healthy controls who will donate blood 11 ml blood monthly for 12 months, or a larger donation of blood on a single occasion. Posters have been prepared to recruit the healthy controls from the Telethon Kids Institute, Subiaco, Western Australia.

12. Research involving ionizing radiation

Not applicable as narrow band UVB radiation is not ionizing radiation.

13. Inclusion Criteria

For inclusion in this study, a participant must meet the following criteria:

- Aged between 18 and 65 years old inclusive.
- Recently diagnosed (<120 days) with a first isolated, well-defined, uni- or multi-focal first demyelinating event (FDE).
- Able to receive their first phototherapy within 120 days of FDE symptom onset.
- An MRI brain scan that is supportive of demyelinating disease (Paty A or Paty B criteria, i.e. the presence of at least four T2 lesions greater than 3 mm, or at least three T2 lesions greater than 3 mm, one of which must be periventricular, respectively).
- An EDSS between 0 6.5 (inclusive)
- Must be able to give informed consent and sign the informed consent form
- Must be able to comply with all study procedures, and attend 24 phototherapy sessions and centres for venepuncture on multiple occasions during and after phototherapy
- If female of child-bearing age, must be willing to use effective contraception
- Must be willing to avoid use of sunbeds
- Must be able to stand in the phototherapy cubicle for up to 5 minutes at a time

14. Exclusion Criteria

Any of the following conditions will exclude a participant from the study:

- Known co-morbid illnesses that might be exacerbated by phototherapy, including lupus erythematosus and xeroderma pigmentosum
- A history of melanoma, multiple non melanoma skin cancers
- Previous prolonged courses of UVB or photochemotherapy (PUVA), or use of sunbeds
- Cardiovascular or respiratory disease that would prevent standing in the treatment cubicle
- Bullous disease
- Use of photosensitizing medications
- Very fair skin that burns with very minimal sun exposure (as judged by the dermatologist involved)
- Current immunosuppressive drug therapy (beta-interferon, glatiramer acetate, natalizumab, mitoxantrone, or other chemotherapy agent specifically for demyelinating disease) prior to CIS diagnosis. (*Note that requirement for immunomodulatory therapy in the course of MS disease management will not exclude patients during follow-up; treatment variables will be collected and analysed in both the intervention and control arms in the planned analysis).
- Current pregnancy, breastfeeding or planning to become pregnant in the next 12 months.
- A second clinical demyelinating event prior to randomisation
- Concurrent diagnosis of other neurological, psychiatric or other disease, which, in the opinion of the investigator, could impair capacity to provide informed consent or interfere with study compliance.
- Current enrolment in another interventional trial

- Any contraindication to MRI scanning or intravenous Gadolinium including:
 - o Cardiac Pacemaker
 - Cardiac Defibrillator
 - o Metal fragments in the eye
 - o Any other non-MRI compatible medical device/implant or medical condition
 - o Previous allergic reaction to Gadolinium
 - o Severe claustrophobia

15. Withdrawal Criteria

Participants will be screened for adverse events during phototherapy, and will cease therapy if they experience a significant or serious adverse event, which, in the opinion of the treating neurologists (Professors [name] and [name]) or the dermatologist ([name]), is related to the treatment.

15.1 Removal/withdrawal of subjects

Participants will be free to withdraw from the study at any time. If they wish to exit the study, an exit visit will be requested to assess any changes in the parameters measured. A cerebral MRI scan will be performed as part of the early termination visit and will substitute for the next protocol-specified MRI scan. Participants will be asked to exit the trial if there is more than one week between phototherapy sessions and they cannot complete 24 phototherapy sessions within 12 weeks. They will be asked to return to the clinic for an early withdrawal/Exit visit.

If a participant develops a confirmed second demyelinating event (confirmed relapse), the participant should be managed by Professors [name] and [name]. Subjects will be withdrawn from UVB phototherapy if they experience a significant or serious adverse event, which, in the opinion of [name] or Professors [name] or [name], is related to UVB phototherapy.

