8.3 Accountability Procedures for UVB phototherapy

Prior to commencing narrow band UVB phototherapy, a risk factor profile including previous phototherapy or PUVA treatment, sun exposure history, occupation, personal and family history of skin cancer, and medication will be ascertained. Upon examination, sun damage and presence of skin disease including skin cancers will be documented. Phototherapy will be given three times/week for eight weeks (24 exposures in total). Phototherapy will be delivered according to the Dundee protocol which is based on the patient's skin type. The starting dose of 20 mJ/cm² is chosen based on knowledge of the skin type and will be well below the likely erythema threshold. All patients will start with 40% increments on their initial dose, which will be reduced to 20% increments after 6 exposures. At each visit the dose given and any adverse effects will be recorded.

If a participant develops a confirmed second demyelinating event (confirmed relapse), the participant should be managed by Professors [name] and [name], or other neurologists associated with the study. Subjects will be withdrawn from UVB phototherapy if they experience a significant or serious adverse event, which, in the opinion of [name] or Professors [name] or [name] or other neurologists associated with the study, is related to UVB phototherapy.

The schedule is to give narrow band UVB phototherapy 3 times a week for 8 weeks Participants will be asked to exit the trial if there is more than one week between phototherapy sessions and they cannot complete 24 phototherapy sessions within 12 weeks. We will ask participants to return to the clinic for an early withdrawal/Exit visit.

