8.6 Endpoints of the study

Primary Endpoints:

- Phototherapy-associated changes in transcriptome profiling in whole blood
- Phototherapy-associated changes in the phenotype of cells in freshly isolated peripheral blood
- Phototherapy-associated changes in T regulatory cells in the peripheral blood as measured by Foxp3 expression and Foxp3 demethylation analysis
- Phototherapy-associated changes to immunological function of cells in the peripheral blood
- Development of a new demyelinating event defined as either
- A confirmed clinical relapse or
- A new cerebral T2 lesion and/or newly Gadolinium-enhancing cerebral lesion at either the 6 month or 12 month MRI scan compared to the study baseline scan.

Secondary Endpoints:

- Baseline to 12 month EDSS change
- Baseline to 12 month change in SF36 Quality of life score
- Baseline to 12 month change in Fatigue score
- Baseline to 12 month cerebral MRI grey matter volume change
- Baseline to 12 month cerebral MRI white matter volume change
- Safety: Adverse Events (including SAE) reported for UVB phototherapy

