10.4.1 The 1 week visit

Members of the Study Team will confirm that no adverse event has taken place due to narrow band UVB exposure. Blood will be collected for measurement of biomarkers and isolation of peripheral blood mononuclear cells for functional assays. Any change in symptoms or medications will be recorded.

10.4.2 Study visits at 1 month, 2 months, 3 months, and 6 months since start of phototherapy (or randomisation into the non-phototherapy group)

Participants will be reviewed as per the study schedule (Appendix 1).

Participants will have an appointment with their neurologist after 3 and 6 months. After 1 and 2 months, participants will meet one of the study team unless any symptoms require neurologist review.

- Blood collection for measurement of biomarkers and isolation of peripheral blood mononuclear cells for functional assays (1, 2, 3 and 6 months)
- Gadolinium-enhanced cerebral MRI (after 3 months if neurologist feels necessary, after 6 months for all participants)
- Clinical evaluations with review of any adverse events, intercurrent medical events and updated concomitant medications (1, 2, 3 and 6 months)
- Serial Questionnaires (6 months, see Appendices).
- KFS, MSFC (1, 2, 3 and 6 months).
- Measures of weight, blood pressure (1, 2, 3 and 6 months). Participants will be asked to remove clothing to allow placement of a blood pressure cuff on their arm
- Saliva collection for EBV measurement

10.4.3 Final Visit 12 months since start of phototherapy (or randomisation into the non-phototherapy group)

Participants will be reviewed by both a neurologist and a member of the study team as per study schedule (Appendix 1, Study schedule).

- Blood collection for measurement of biomarkers and isolation of peripheral blood mononuclear cells for functional assays
- Gadolinium-enhanced cerebral MRI
- Clinical evaluations with review of relapse history, adverse events, intercurrent medical events and updated concomitant medications
- EDSS, KFS, MSFC.
- Fatigue Severity Scale, SF-36, Exit questionnaires (See Appendices).

- Anthropometric measurements (weight, height, waist and hip circumference), blood pressure. Participants will be asked to remove clothing to allow waist and hip measurement and placement of a blood pressure cuff on their arm
- Eye/skin/hair colour assessment
- Assessment of skin reflectance and preparation of a silicone cast of the back of the hand
- Saliva collection for EBV measurement

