10.4.5 Early Termination Visit

If a participant exits the study for any reason (including inability to complete 24 phototherapy sessions in 12 weeks), an early termination visit will be organised as soon as possible.

This visit will comprise

- Blood collection for measurement of biomarkers and isolation of peripheral blood mononuclear cells for functional assays
- Gadolinium-enhanced cerebral MRI (exit scan)
- Clinical evaluations with review of relapse history, adverse events, intercurrent medical events and updated concomitant medications
- EDSS, KFS, MSFC
- Fatigue Severity Scale, SF-36, Exit questionnaires
- Anthropometric measurements (weight, height, waist and hip circumference), blood pressure

Eye/skin/hair colour assessment

Assessment of skin reflectance and preparation of a silicone cast of the back of the hand.

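### The rule asking UVB participants to leave the trial for incomplete phototherapy applies to one arm only and loses or mistimes that arm's 6- and 12-month outcomes

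*Protocol*

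**What the plan says.** Protocol sections 8.3 and 15.1 carry the same rule. It has two conditions that must both hold. The first is in these words: "Participants will be asked to exit the trial if there is more than one week between phototherapy sessions". The second, joined to it, is that "they cannot complete 24 phototherapy sessions within 12 weeks". Section 8.3 continues: "We will ask participants to return to the clinic for an early withdrawal/Exit visit". Section 10.4.5 confirms that this is an exit from the study; its opening words are "If a participant exits the study for any reason (including inability to complete 24 phototherapy sessions in 12 weeks".

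On imaging, section 15.1 states: "A cerebral MRI scan will be performed as part of the early termination visit and will substitute for the next protocol-specified MRI scan". Section 10.4.2 schedules the follow-up MRI "after 3 months if neurologist feels necessary, after 6 months for all participants", so after an exit within the first 12 weeks the next scan due for everyone is at 6 months.

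The MRI part of the demyelinating-event primary endpoint (section 8.6) is tied to dates: "A new cerebral T2 lesion and/or newly Gadolinium-enhancing cerebral lesion at either the 6 month or 12 month MRI scan". The secondary endpoints there (EDSS, SF-36, fatigue, grey and white matter volume) are changes from baseline to 12 months. Section 19.1 admits UVB participants to the intention-to-treat analysis once they have had six sessions.

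**The concern.** Missing phototherapy sessions is a departure from treatment. The rule turns it into departure from the trial, and it can do so only in the arm that has sessions. Neither section 10.4.5 nor the schedule in Appendix 1 describes any contact after the exit visit. A UVB participant who meets the rule therefore has no 12-month scan, no recorded later relapse, and no 12-month EDSS, SF-36, fatigue, volume or biomarker measurement. The scan at about month 3 takes the place of the 6-month one.

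With six or more sessions, that participant still belongs to the analysis set, but with outcomes that are missing or taken at a different time from the controls'. Data that were never collected cannot be recovered by an analysis plan, so this has to be settled in the protocol.

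**Working it through.** **What the text fixes**

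| Situation | What ends | Who can meet it |
|---|---|---|
| Gap of more than one week and 24 sessions not achievable in 12 weeks (8.3, 10.4.5, 15.1) | Trial participation | UVB arm only |
| Significant or serious adverse event judged related to UVB (8.3, 15, 15.1) | Phototherapy | UVB arm only |
| Participant's own wish to leave (15.1) | Trial participation | Both arms |

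The protocol thus already separates stopping phototherapy from leaving the trial in the adverse-event case. However, a participant stopped early for an adverse event will also have a gap of more than a week and will not complete 24 sessions, so read literally meets the exit rule too. The passages do not say which applies.

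**Size: inputs**

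- From the protocol: 30 per arm; scans for all at 6 and 12 months; new MRI lesions in 90% over 1.5–2 years (sections 8.7 and 19.3).
- Assumed, because the protocol gives no figure: a proportion *q* = 10%, 20% or 30% of the UVB arm exits at month 3 and no control exits; no treatment effect; constant hazard; exit unrelated to prognosis; MRI events only; 12-month risk *r* = 50%, 70% or 90%.

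The protocol's 90% implies 12-month risks inside that range: 1 − 0.1^(12/18) = 78.5% if reached at 18 months, and 1 − 0.1^(12/24) = 68.4% if at 24 months.

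**Crude 12-month proportion.** Risk by the exit scan is r3 = 1 − (1 − r)^(3/12). The false advantage to UVB is q × (r − r3).

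| r | r3 | q = 10% | q = 20% | q = 30% |
|---|---|---|---|---|
| 50% | 15.9% | 3.4 points | 6.8 | 10.2 |
| 70% | 26.0% | 4.4 | 8.8 | 13.2 |
| 90% | 43.8% | 4.6 | 9.2 | 13.9 |

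With the protocol-implied risks, r3 is 31.9% (for 78.5%) or 25.0% (for 68.4%), and the result is 4.7, 9.3 and 14.0 points or 4.3, 8.7 and 13.0 points.

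**Log-rank, the test section 19.4.1 names.** Control lesions can be dated only to month 6 or 12. An exiting UVB participant's lesion is dated to month 3; one without a lesion is censored there. Simulation under no effect (30 per arm, 3,000 trials per cell, each UVB participant exiting with probability *q*); positive z is against UVB:

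| r | q = 10%: mean z, rejection | q = 20% | q = 30% |
|---|---|---|---|
| 50% | 0.12, 4.8% | 0.19, 5.4% | 0.35, 5.6% |
| 70% | 0.16, 5.4% | 0.33, 6.0% | 0.51, 7.5% |
| 90% | 0.31, 5.3% | 0.64, 10.2% | 0.94, 15.3% |

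Allowing for simulation error, this is a mean z of about 0.1–0.9 and two-sided rejection of about 5–16% at a nominal 5%.

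**Few exits.** At r = 70%, one or two exits in 30 give 1/30 × 44.0 = 1.5 or 2/30 × 44.0 = 2.9 points on the crude proportion. In the log-rank test the mean z is about 0.1 or less and rejection stays at about 5%.

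**The case against.** The trigger is narrower than the first condition alone suggests. Both conditions must hold, an 8-week course is allowed 12 weeks, participants are asked rather than compelled to leave, and entry requires the ability to attend 24 sessions. Nothing in the protocol supports any particular exit rate, and with one or two exits the effect is small. All of that stands.

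A reader might infer that the rule creates a spurious benefit of about 9 points, close to the planned 10% reduction. The documents do not support this. It needs an assumed 20% exit rate and a crude proportion that counts event-free exits as event-free for a full year. Section 19.4.1 places this endpoint under proportional hazards, Kaplan–Meier and log-rank methods, where the shift is modest in most scenarios and goes against UVB.

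A reader might also infer that the sickest patients are lost. That is plausible but not shown. Relapse leads to neurological management, not exit, and a relapse before exit already counts as an event.

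Nor does the rule contradict every intention-to-treat analysis: section 19.1 keeps participants with six sessions. What the rule does is withhold outcome data that such an analysis needs.

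The loss is also partial. The exit visit collects blood, MRI, EDSS, MSFC, fatigue and SF-36, and four of the five primary endpoints are biomarkers with earlier samples available to the mixed models.

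Finally, the scan-substitution sentence follows the text on voluntary withdrawal and applies to both arms. But section 10.4.5 provides one early termination visit for every exit, so the substitution also reaches the one-arm exits.

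**Conclusion.** The point holds as a defect of design. The rule removes participants from follow-up for a treatment departure that only the UVB arm can have, and its exit scan replaces a scan on which the primary endpoint depends. That follows from the text and needs no assumed figure.

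The size is uncertain. It rests on an exit rate the protocol does not give, a constant hazard, exit at month 3 and exit unrelated to prognosis. Under 10–30% exits and a 12-month risk of 50–90%, the named log-rank analysis is moved against UVB by a mean z of about 0.1–0.9, with rejection of about 5–16%. The largest distortion needs nine exits in 30 and a 90% risk at 12 months. A crude proportion, if used, errs the other way by about 3–14 points. Because the direction depends on the analysis, the bias cannot be dismissed as conservative. Informative exit would add to it, but the documents do not establish that.

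**What to change.** In sections 8.3, 10.4.5 and 15.1, separate stopping phototherapy from leaving the trial. For example: *Participants who miss or stop phototherapy for any reason remain in the trial and attend all remaining visits, blood collections and the 6- and 12-month MRI.* Reserve the early termination visit for participants who withdraw from follow-up or withdraw consent. Replace the substitution sentence with a statement that any exit MRI is analysed at its actual date and not as the 6- or 12-month scan.

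Reconcile these sections with the adverse-event text, which withdraws participants only from phototherapy. The rule on when phototherapy itself stops is not at issue and no change to it is proposed.

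The cost is an amendment to the protocol, to the consent wording where it repeats the rule, and continued follow-up of what may be a few participants at visits and scans already in the schedule. The protocol does not show how these are budgeted.

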15.2 Early termination of the study

The study may be terminated prematurely by the Co-ordinating Principal Investigator or their designee, after consultation with the Steering committee and the Data Safety Monitoring Board if:

- The number and/or severity of adverse events justify discontinuation of the study
- New data become available which raise concern about the safety of UVB phototherapy, so that continuation might cause unacceptable risks to subjects.

In addition, the Co-ordinating Principal Investigator reserves the right to discontinue the trial prior to inclusion of the intended number of subjects, but intends only to exercise this right for valid scientific or administrative reasons.

After such a decision, the Co-ordinating Principal Investigator must contact all participating subjects within two weeks, and written notification must be sent to the Ethics Committee.

16. Other Participants

Not relevant

17. Efficacy

There are many patients with psoriasis who gain large clinical benefits from narrow band UVB phototherapy. The dermatologists talk about phototherapy 'junkies'. With no documented side effects for patients with psoriasis, we propose on the epidemiological data and the murine studies, that UVB phototherapy will benefit patients with CIS.

Efficacy Assessments:

- Fatigue Severity Score (FSS)
- EDSS, KFS, and MSFC
- SF-36v2 Quality of Life Questionnaire
- Lifestyle Questionnaires

18. Adverse Events (AE) and Serious Adverse Events (SAE)

Members of the investigator team are responsible for the detection and documentation of events meeting the criteria and definition of an adverse event (AE) or a serious adverse event (SAE) as provided in this protocol.

18.1 Definition of an Adverse Event (AE)

Any untoward medical occurrence in a participant, temporally associated with delivery of narrow band UVB phototherapy, whether or not considered related to the UVB phototherapy.

Examples of an AE include:

- Exacerbation of a chronic or intermittent pre-existing condition including either an increase in frequency and/or intensity of the condition.
- New conditions detected or diagnosed after administration of narrow band UVB phototherapy even though it may have been present prior to the start of the study.
- Signs, symptoms, or the clinical sequelae of a suspected interaction.

18.2 Definition of a Serious Adverse Event (SAE)

A serious adverse event is any untoward medical occurrence that as a result of UVB phototherapy:

a) results in death

- b) is life threatening^b
- c) requires inpatient hospitalisation or prolongation of an existing hospitalisation.^C
- d) results in disability/incapacity^d, or
- e) is a congenital abnormality / birth defect.
- ^b Note: The term 'life-threatening' in the definition of 'serious' refers to an event in which the subject was at risk of death at the time of the event. It does not refer to an event, which hypothetically might have caused death if it were more severe.
- ^C Note: In general, hospitalisation signifies that the subject has been detained (usually involving at least an overnight stay) at the hospital or emergency ward for observation and/or treatment that would not have been appropriate in the physician's office or out-patient setting. Complications that occur during hospitalisation are AEs. If a complication prolongs hospitalisation or fulfils any other serious criteria, the event is serious. When in doubt as to whether 'hospitalisation' occurred or was necessary, the AE should be considered serious.

Hospitalisation for elective treatment of a pre-existing condition that did not worsen from baseline is not considered an AE.

^d Note: The term disability means a substantial disruption of a person "s ability to conduct normal life functions. This definition is not intended to include experiences of relatively minor medical significance such as uncomplicated headache, nausea, vomiting, diarrhoea, influenza, and accidental trauma (e.g. sprained ankle) which may interfere or prevent everyday life functions, but do not constitute a substantial disruption

Hospital admission for the purpose of treating an MS relapse will not be considered as a SAE, as it is an expected occurrence in participants with CIS. Medical and scientific judgement should be exercised in deciding whether reporting is appropriate in other situations, such as important medical events that may not be immediately life-threatening or result in death or hospitalisation, but may jeopardise the subject or may require medical or surgical intervention to prevent one of the other outcomes listed in the above definition.

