8.1 Participants in the PhoCIS Trial

We will recruit 60 patients who have had a first demyelinating event (i.e. diagnosed with CIS). Of these, 30 will receive phototherapy in addition to standard-of-care, while the remaining 30 will receive standard-of-care treatment. All participants will wear a UVB dosimeter.

As part of standard-of-care, all patients will receive sufficient vitamin D supplementation to achieve serum 25(OH) D levels of ≥ 100 nmol/L.

Patients with CIS will be approached by Professors [name] or [name] to join the trial.

There will be two additional groups donating blood. In the first group, 10 age and sex matched healthy individuals in Perth will donate 11 ml blood monthly for 12 months for selected biomarker analysis (transcriptome analysis of cells in whole blood and serum 25(OH)D levels). Measurement of these particular biomarkers of these healthy controls from the same city as the CIS patients will allow precise comparison of the relative extent of change in expression of those biomarkers by UVB phototherapy, and during the different seasons of the year. Additionally, this group of healthy controls will be required to fill out the lifestyle questionnaires (see Appendix) at the beginning of the study, then again at the 6 and 12 month visits. The healthy individuals donating blood monthly for 12 months will be recruited by advertisement from the staff at the Telethon Kids Institute in Subiaco, Western Australia. They will not be paid.

In the second group, up to 40 age and sex matched healthy individuals in Perth will donate up to 45 ml blood on a single occasion. The profile of their cells will be compared with those from blood taken from the study participants with CIS at baseline. They will not be paid.

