18.8.2 Assessment of Causality

The Co-ordinating Principal Investigator is obligated to assess the relationship between the intervention and the occurrence of each AE/SAE, in consultation with Professors [name] and [name], and [name]. Alternative causes, such as natural history of the underlying diseases,

concomitant therapy, other risk factors, and the temporal relationship of the event to the administration of narrow band UVB phototherapy will be considered and investigated.

The causal relationship to UVB phototherapy should be assessed using the following classifications:

Not Related In the Investigator's opinion, there is not a causal relationship between UVB

phototherapy and the adverse event.

Unlikely The temporal association between the adverse event and UVB phototherapy is

such that UVB phototherapy is not likely to have any reasonable association with

the adverse event.

Possible The adverse event could have been caused by the study participants's clinical

state or UVB phototherapy.

Probable The adverse event follows a reasonable temporal sequence from the time of

UVB phototherapy, abates upon discontinuation of UVB phototherapy and cannot be reasonably explained by the known characteristics of the study

participants's clinical state.

Definitely The adverse event follows a reasonable temporal sequence from the time of

UVB phototherapy or reappears when UVB phototherapy is reintroduced.

There may be situations when an SAE has occurred and a member of the study team has minimal information to include in the initial report to the Co-ordinating Principal Investigator, and the Data Safety Monitoring Board. However, it is very important that the member of the study team always makes an assessment of causality for every event prior to transmission of the SAE form to the Co-ordinating Principal Investigator. Investigators may change their opinion of causality in light of follow-up information, amending the SAE form accordingly. The causality assessment is one of the criteria used when determining regulatory reporting requirements.

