19.2 Safety monitoring and analysis

The independent Data Safety Monitoring Board will review all serious adverse events individually and unblinded, all reported adverse events in summary format and all study withdrawals. The Data Safety Monitoring Board may recommend cessation of the study due to safety concerns at any time. It is envisaged that the Data Safety Monitoring Board will meet 6-monthly by teleconference (or as required), to be convened by the Co-ordinating Principal Investigator. The Data Safety Monitoring Board will consist of an independent neurologist ([name]), a dermatologist and an endocrinologist.

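### The SAE definition requires causation by UVB and the AE definition requires UVB delivery, so a serious event in a control, or one not attributed to UVB, can bypass individual safety review

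*Protocol*

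**What the plan says.** **Definitions.** Section 18.1 describes an AE as an untoward occurrence "temporally associated with delivery of narrow band UVB phototherapy, whether or not considered related to the UVB phototherapy". Section 18.2 begins "A serious adverse event is any untoward medical occurrence that as a result of UVB phototherapy" and then lists the serious outcomes. The opening of section 18 makes investigators responsible for detecting and documenting events that meet these definitions, and 18.3 refers abnormal laboratory findings back to them.

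**Who receives UVB.** Section 8.1: "Of these, 30 will receive phototherapy in addition to standard-of-care, while the remaining 30 will receive standard-of-care treatment".

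**Collection.** Section 10.5 has every AE reported from consent to final follow-up entered in the case report form. Section 18.4 also starts at consent and says each participant is monitored. Appendix 1 schedules AE reporting at every visit from week 1 onward, under a heading that covers both randomised groups. Against this, the 1-week visit (10.4.1) checks only for events due to UVB, and the safety endpoint (8.6) is worded for events reported for UVB.

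**Causality.** Section 18.8.2 has causality rated for each AE and SAE on a scale that starts at *Not Related*. Section 18.7 treats causal relation and seriousness as two separate conditions for expedited reporting.

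**Oversight.** Under 18.6, an SAE goes to the monitoring board within 24 hours and is then reported to the ethics committee. Under 19.2 the board "will review all serious adverse events individually and unblinded"; it also receives reported AEs in summary and all withdrawals.

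**The concern.** Seriousness and causality are separate judgements. Seriousness describes the outcome of the event; causality is an opinion about its source, which can be wrong and can change. Section 18.2 merges them, so the team must decide that UVB caused a death or hospital admission before the event counts as an SAE. Independent review exists partly to catch events that the team did not attribute to treatment, and under 18.2 those are the events that miss individual review.

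The AE definition has a related gap. Controls receive no UVB, so nothing that happens to them can be associated in time with its delivery. Staff who follow section 18 and staff who follow 10.5 would record different events. An event not recorded during the trial cannot be reliably recovered at analysis, so this cannot be left to a statistical analysis plan.

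**Working it through.** There is no figure to reproduce. The check is a reading of which events the definitions admit. Section 18.1 gives no time window, so I assume that any event after a patient's first session counts as "temporally associated with delivery of narrow band UVB phototherapy".

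| Event | AE under 18.1 | SAE under 18.2 |
|---|---|---|
| UVB arm, after first session, not serious, related | in | not applicable |
| UVB arm, after first session, not serious, unrelated | in | not applicable |
| UVB arm, after first session, serious, attributed to UVB | in | in |
| UVB arm, after first session, serious, not attributed | in | **out** |
| UVB arm, between consent and first session | **out** | **out** |
| Control arm, any event | **out** | **out** |

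The control arm is 30 of 60 patients, so 30/60 = 50% of those randomised can contribute no event on the literal wording.

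**Comparison with the other sections:**

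- 10.5 and 18.4 start at consent and are not limited by arm. Under 18.1, nothing before the first session and nothing in a control qualifies.
- Appendix 1 schedules AE reporting for both groups. Under 18.1, the control entries could only be empty.
- 18.8.2 offers *Not Related* for SAEs. No event that satisfies 18.2 could be given that rating.
- 18.7 requires an expedited event to be both causal and serious. If 18.2 stands, the first condition adds nothing.
- 18.6 allows the causality rating of an SAE to be amended after reporting. Under 18.2, an event re-rated as unrelated would never have been an SAE.

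**What depends on the label.** The 24-hour notice and the ethics committee report (18.6) and individual board review (19.2) all apply to SAEs. A serious event in the UVB arm that is not attributed to UVB remains an AE and reaches the board in summary, at a meeting envisaged every six months or as required. A serious event in a control reaches that summary only if staff follow 10.5 and 18.4 rather than 18.1.

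**Secondary wording point.** In 18.8.2, *Probable* requires a reasonable time sequence, abatement when UVB stops, and no reasonable explanation from the patient's clinical state. *Definitely* requires a reasonable time sequence from "UVB phototherapy or reappears when UVB phototherapy is reintroduced". Because the two conditions are joined by *or*, timing alone satisfies the highest category while failing the one below it.

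**The case against.** The best defence is that the protocol read as a whole intends both arms to be covered. Sections 10.5 and 18.4 and Appendix 1 say so. Section 18.2 itself excludes hospital admission for MS relapse, an exclusion that would be largely redundant if only UVB-caused events could be SAEs. That is good evidence of intent and makes capture of control-arm AEs likely in practice. It does not remove the contradiction, because section 18 ties the duty to document to the definitions, and no other section redefines an SAE.

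Several stronger readings are tempting, and the documents do not support them:

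- *All unrelated events are excluded.* Section 18.1 admits AEs "whether or not considered related to the UVB phototherapy". Only unrelated serious events lose their label.
- *Safety cannot be compared between arms.* Control AE data may well exist under 10.5, 18.4 and Appendix 1; completeness is at risk. The protocol also promises no between-arm safety test: aim 5 and the endpoint concern UVB.
- *The board sees only events attributed to UVB.* Section 19.2 also gives it all reported AEs in summary and all withdrawals. The gap is in prompt notice and individual review.
- *The causality scale distorts withdrawal and expedited reporting.* Those rest on an opinion that the event is related (8.3, 15, 15.1) and on causal relation (18.7). Neither is stated to turn on *Probable* versus *Definitely*.
- *Recording adverse effects at each of 24 sessions, when the arms share three visits in those 8 weeks, is an error.* Recording effects at treatment sessions is ordinary monitoring. All participants may also report symptoms within 48 hours and attend unscheduled visits (10.4.4).

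**Conclusion.** Sections 18.1 and 18.2 are wrong as written and conflict with 10.5, 18.4, 18.7, 18.8.2 and Appendix 1. On the literal wording, events in 30 of 60 patients, events before the first session, and serious events not attributed to UVB all miss the SAE route. The consequence is bounded: such an event can bypass the 24-hour notice and individual board review and would be seen at most in the AE summary, and like-for-like capture across arms is not assured. No primary endpoint depends on this.

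The conclusion assumes that staff apply the definitions as section 18 directs. If they follow 10.5 and 18.4 instead, control AEs are recorded, but the SAE gap remains because 18.2 alone defines that label. The conflict over *Definitely* is a minor wording fault with no demonstrated effect on any decision.

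**What to change.** 1. **18.1:** define an AE as any untoward medical occurrence in a participant of either arm, from consent to the final visit, related to UVB or not.
2. **18.2:** delete the phrase that makes the serious outcome a result of UVB. Leave causality to 18.8.2.
3. **18.6 and 19.2:** state that SAEs from both arms go to the monitoring board.
4. **10.4.1 and 8.6:** align the 1-week check and the safety endpoint with 10.5 and 18.4, so that they cover all AEs in both arms.
5. **18.8.2 (secondary):** reconcile *Definitely* with *Probable* so that timing alone does not meet the higher category. Re-exposure should not be made mandatory, since *Definitely* would then be unattainable for a death or for a patient who stopped UVB and was not re-exposed.

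The cost is changes to protocol and case report form wording and a few more SAE forms. Visits, sample size and efficacy analyses are unaffected.
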